Aim 2: Adults aged 21 and older who reside in any Ohio county and smoke at least 5 cigarettes per day will be considered for this project. Smokers who use other tobacco products (e.g., SLT, electronic cigarettes) > 10 days a month will be ineligible because our goal is to characterize the abuse liability of NPs among those who exclusively or primarily smoke cigarettes.

Inclusion	Exclusion
Age 21 years or older	Use tobacco products other than cigarettes >10 days per month.
Willing to complete study procedures, including abstaining from all tobacco, nicotine, and marijuana for 12 hours before clinic visits	Use NP in the past 3 months
Ability to read and speak English	Unstable or significant psychiatric conditions (past and stable conditions will be allowed)
Smoke at least 5 cigarettes per day for the past 30 days	Pregnant, planning to become pregnant, or breastfeeding
	History of cardiac event or distress within the past 3 months
	Currently attempting to quit all tobacco use

3. Study Procedures

Clinic Visits

Informed consent

The participant will arrive at the CTR and meet a member of the research staff in the lobby. The research staff member will escort the subject to a private lab room and review the informed consent form (including a description of the nature, purpose, risks, and benefits of the study). The subject will receive an oral and written explanation of the study. The voluntary nature of the study and the participant's right to withdraw at any time will be stressed during the consent process; a copy of the informed consent will be provided to the participant either electronically or physically at the time of consent for them to keep. Informed consent will be collected by IRB-approved study personnel and stored electronically in the secure database, REDCap.

Recruitment scripts and materials, consent forms, and all study procedures will be approved by the OSU Institutional Review Board. All participants will provide written consent before any study procedures are performed.

Randomization

After participants consent to the study, their visit order will be randomized. Randomization will be counterbalanced and cannot be changed once it is completed. Randomization in Aim 1 involves the 3mg, 6mg, or regular brand of cigarettes while Randomization in Aim 2 involves the 3mg tobacco-derived NP and 2 synthetic NPs.

Obtain baseline exhaled CO test

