Participants will need to abstain from tobacco and nicotine products for ≥ 12 hours prior to their study visit. To check for abstinence from tobacco, participants will perform exhaled carbon monoxide testing ($eCO < 10\text{ppm}$) and confirm via self-report that they have not used any other nicotine products over the last 12 hours.

Pregnancy Test

All subjects capable of becoming pregnant will need to take and produce a negative pregnancy test in order to proceed further.

Pre-intervention questionnaire to be administered

This questionnaire will assess sociodemographics, tobacco use history, NP use history, and nicotine dependence. These questionnaires will be administered during Visit 1.

IV line insertion

Because blood draws will occur at set intervals, an IV line will be inserted by a trained staff nurse.

Blood draw to obtain baseline plasma nicotine levels

Next, participants will be reminded that in addition to the exhaled CO test, their abstinence will be confirmed at the time of visit via blood plasma nicotine analysis. 3 mL venous blood sample will be collected for later analysis to confirm abstinence. This blood draw will also be used to establish baseline plasma nicotine levels to estimate total nicotine delivery.

Administer intervention

Aim 1: The participant will receive a 3mg NP, 6mg NP, or be asked to smoke one cigarette of their usual brand depending on the randomization assignment. If smoking a cigarette, participants will be asked to smoke one cigarette following a standardized puffing protocol: they will take one puff every 30 seconds for 5 minutes. If using an NP, participants will be asked to place the pouch between their upper lip and gum and leave it in place for 30 minutes.

Aim 2: The participant will receive a 3mg tobacco-derived NP or a 3mg synthetic NP on randomization assignment. Participants will be asked to place the pouch between their upper lip and gum and leave it in place for 30 minutes.

Peri-intervention questionnaire to be administered

The QSU and MNWS surveys will be administered while at each blood draw interval of 0, 5, 15, 30, 60, and 90 minutes.

Post-intervention questionnaire to be administered

Measures of product appeal and behavioral intentions will be assessed after the participant has the cigarette or NP (Aim 1) or the tobacco-derived vs. synthetic NP (Aim 2).

Schedule return visit and provide gift card for participation

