Schedule return visit per subject and interviewer availability that is >2 days after the current visit. Provide \$100 via Clincard for their participation out of the up to \$350 possible. If it is their last visit has been completed within 1 month from consent, they will receive \$150 during their last visit.

Post-Enrollment Survey

6 months after enrolling, participants from Aims 1 and 2 will be recontacted via phone, text, and email for the opportunity to participate in a short online REDCap survey. Participants will complete a short consent addendum and respond to survey questions regarding their current tobacco product use and opinions surrounding nicotine pouches. For their time, they will receive a \$10 Amazon gift code.

Procedure Manual

Study procedures, including conducting pregnancy tests, blood draws, blood processing and analysis, gift card administration, and other procedures will be thoroughly explained in the study procedure manual.

4. Study Administration

Randomization, Blinding, and Unblinding

Participants will be randomized within the secure database, REDCap. The randomization piece involves at which of the 3 visits they are to use each product (Aim 1: 3mg NP, 6mg NP, or their own usual brand cigarette and Aim 2: the tobacco-derived 3mg tobacco-derived NP or the 3mg synthetic pouches). Participants will be blinded during study visits and at the end of their third visit will be informed which product they had at each visit.

Study Timelines, Number of Sites, and Enrollment

Participant Timeline

There will be a total of 3 study visits and 1 online survey opportunity 6 months after the completion of the final study visit. The study timeline for each participant will vary. Clinic visits can be completed in as little as a week and a half or as long as 2 months, but will ideally be completed within 3 week's timeframe for retention and administrative purposes. The study visits will take approximately 3 hours each. The online survey will take approximately 10 minutes to complete and will be offered 6 months after completing the final visit.

Duration of Study

We anticipate the clinical trial to take six months to complete. After that, we anticipate that it will take 1-1.5 years to clean and analyze data and disseminate results.

Total Number of Study Sites

All recruitment and enrollment activities will be completed within the CTR.

Total Number of Subjects Projected

55 subjects will be enrolled and each subject must meet I/E criteria.

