Data will be summarized descriptively. For hypothesis testing, we will use linear or logistic mixed effects regression models (with a random subject effect) to assess the main effects of product on plasma nicotine delivery, subjective effects, and behavioral intentions. Model assumptions will be checked, and variables will be transformed as needed. Missing data will not be imputed as likelihood-based linear mixed models will yield valid inference under missing at random assumptions. Models will control for age, sex, and other tobacco use if these features are not balanced by randomization. The same analysis strategy will be used for both aims. We calculated power for Aim 1 based on a repeated measures ANOVA comparing mean total nicotine delivery and maximum plasma nicotine concentration across 3 conditions; existing literature on differences in nicotine delivery across SLT products, including NPs, facilitates the use of this outcome for a power analysis.⁹ With a total sample size of only 20 participants and a Bonferroni-adjusted alpha of 0.017, we would have 84% power to detect a mean difference in total nicotine delivery of 25.7 ng/mL and 99% power to detect a mean difference of maximum nicotine concentration of 7.0 ng/mL between products.⁹ To account for attrition and the potential need for a larger sample size to detect differences in more subjective outcomes, we will recruit a

sample of 40 participants. For Aim 2, there are no known data to estimate effect sizes and thus to conduct power analyses. The sample size of 15 participants is intended to provide these data for future research.

5. Safety Management, Risks, and Benefits

Safety Management

Clinical Adverse Events

Clinical AE will be assessed by study staff at each study visit via participant self-report and managed immediately. Clinical AE may be related to nicotine overdose or the blood draw. Signs of nicotine overdose include nausea, vomiting, headache, presyncope, tachycardia, and disrupted sleep. With the blood draw, there is a slight risk of bruising, discomfort, and infection with blood draw. Study staff will be trained to recognize these signs and subjects will be encouraged throughout the visit to self-report any AE. In the event of a medical emergency, study staff will be advised to call 911 on the subject's behalf.

AE Reporting

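### The crossover model has no visit-number term: for linear models of outcomes with one value per visit, any shared visit-to-visit shift widens the reported standard errors (minor, inexpensive to fix)

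*Combined protocol and SAP*

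**What the plan says.** The Randomization section under Study Procedures states: "After participants consent to the study, their visit order will be randomized. Randomization will be counterbalanced and cannot be changed once it is completed". The Randomization, Blinding, and Unblinding section confirms that order is all that is allocated: "The randomization piece involves at which of the 3 visits they are to use each product". The number of orders used is not stated.

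Statistical Considerations is the only analysis text. It specifies "linear or logistic mixed effects regression models (with a random subject effect) to assess the main effects of product", covering plasma nicotine, subjective effects and intentions, and adds "The same analysis strategy will be used for both aims". The only other covariates are conditional: "Models will control for age, sex, and other tobacco use if these features are not balanced by randomization". No visit, period or sequence term appears anywhere in the document.

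Three further passages bear on the point:
- Ratings are repeated at each visit: "Measures of product appeal and behavioral intentions will be assessed after the participant has the cigarette or NP".
- Both aims list as an exclusion "Use NP in the past 3 months".
- The Aim 1 sample was enlarged "To account for attrition and the potential need for a larger sample size to detect differences in more subjective outcomes".

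**The concern.** A random subject effect removes differences between people. It does not remove a shift that everyone shares between visit 1 and later visits. Age and sex are constant within a person, so adjusting for them does not remove it either. Such a shift therefore goes into the residual variance from which every product standard error is computed.

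A shift is most plausible for appeal and intention ratings. In Aim 2 all three products are pouches and recent pouch users are excluded, so visit 1 is everyone's first recent pouch use. In Aim 1 one of the three visits is a cigarette, so visit number tracks first pouch use only partly.

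What is at stake is the width of intervals and the power for the subjective outcomes, where the plan itself expects to need more participants, and the variance estimates from Aim 2, whose 15 participants are there to inform later studies.

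**Working it through.** **1. The plan's own figures.** The alpha reproduces: 0.05/3 = 0.0167, rounded to 0.017. The stated power (84% for 25.7 ng/mL total delivery, 99% for 7.0 ng/mL maximum concentration, both at 20 participants) cannot be recomputed, because no SD or within-person correlation is given. Solving backwards (two-sided test assumed) implies a paired-difference SD of 31.4 to 34.0 ng/mL for total delivery and 6.1 to 6.6 ng/mL for maximum concentration. These are implied values, not a check of the power.

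**2. Inputs.** From the documents: three visits, 40 participants (Aim 1), 15 participants (Aim 2; the Study Outline says 20), alpha 0.017. Assumed, because the documents are silent: the visit shift s in within-person residual SDs, applied to visit 1 only, and a product contrast of 0.75 SD.

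**3. Inflation of the standard error** (linear model, one value per visit, balanced orders, complete data). Omitting visit adds n·Σc² to the residual sum of squares, where c are the centred visit effects. The residual has 2(n − 1) degrees of freedom. A visit-1 shift s gives c = 2s/3, −s/3, −s/3, so Σc² = 2s²/3 and

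variance ratio = 1 + n·s² / [3(n − 1)]; SE ratio = its square root.

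| n | s = 0.25 | s = 0.5 | s = 1 |
|---|---|---|---|
| 15, variance | 1.022 | 1.089 | 1.357 |
| 15, SE | 1.011 | 1.044 | 1.165 |
| 40, variance | 1.021 | 1.085 | 1.342 |
| 40, SE | 1.011 | 1.042 | 1.158 |

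Using 20 instead of 15 for Aim 2 changes little: at s = 1 the variance ratio is 1 + 20/57 = 1.351, an SE ratio of 1.162.

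**4. Simulation at n = 15** (three orders in a Latin square, nominal 5%). The true sampling SD of a contrast is about 0.365 (√(2/15)) with or without the term. For s = 0.5 / 1 the mean reported SE is about 0.378 / 0.422 without the term and about 0.361 with it. Type I error is about 4.1% / 2.4% without the term and about 5% with it.

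**5. Power at n = 40** (alpha 0.017, contrast 0.75 SD, shift shared by all products). The contrast's SE is √(2/40) = 0.2236, so the noncentrality is 0.75/0.2236 = 3.354.
- With visit (76 df): 81.7%.
- Without visit (78 df, residual variance drawn as noncentral chi-square): about 81% / 79% / 70% for s = 0.25 / 0.5 / 1.

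**6. If the Aim 1 effect is first-pouch novelty.** Here the shift falls on each person's first pouch visit (six balanced orders, n = 42). Power for 3 mg against 6 mg at shifts of 0.5 / 1 SD is 82.1% / 75.8% without the term and 82.8% / 79.4% with it. The term recovers only 1 to 4 points.

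**7. Imperfect balance.** Forty is not divisible by 3 or 6. With the most even six-order split and complete data, the largest distortion of any contrast at s = 0.5 / 1 is 0.025 / 0.05 SD. The visit term removes it.

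**8. Aim 1 nicotine delivery.** With the implied SD and 25.7 ng/mL at n = 40, power is 99.4% with the term. It is 98.6% without it when values drift by 0.5 SD per visit.

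**9. Logistic models.** With six balanced orders and 60,000 simulated people, omitting visit shrank the product coefficient by 6% for an assumed visit-1 shift of 1 logit and by 17% for 2 logits.

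**10. Measures taken six times per visit.** Craving, withdrawal and plasma nicotine are collected at 0, 5, 15, 30, 60 and 90 minutes. Suppose the raw values enter a model with only a random subject effect, at n = 15 with an assumed person-by-visit SD of 0.5 to 1 times the within-visit noise. Type I error at nominal 5% was then roughly 14% to 34% without a visit term and 18% to 35% with one.

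**The case against.** The strongest case against is that nothing in the documents shows a visit effect. At 0.25 SD the cost is about 1% in the standard error and under one point of power. The 0.75 SD contrast is also assumed. The largest Aim 1 loss (82% to 70%) needs a full 1 SD shift that applies equally to the participant's usual cigarette, whereas the natural mechanism is first pouch use, for which the term helps little. Subjective effects and intentions are listed as exploratory in both aims. For linear models with counterbalanced orders the planned tests remain valid. All of this stands, and it limits the weight of the point.

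A reader might infer more: that product comparisons are biased, that false positives rise, or that true precision is lost. For linear models with one value per visit the documents do not support this. Order is counterbalanced, so estimates are essentially unbiased, their true sampling SD is unchanged, and the error is on the conservative side. Had order been randomised without balance, the wider SE would have matched a real loss of precision, but that is not the plan.

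The opposite generalisation, that omitting visit always errs safely, is also too broad. It does not describe logistic models (step 9) or raw within-visit series (step 10). The plan does not say whether those series are reduced to one value per visit, so neither an inflated error rate nor its absence can be read from the text.

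**Conclusion.** The omission is real and specific, and its weight is minor. For linear models of outcomes with one value per visit, reported standard errors would be too wide by about 1%, 4% or 16% under assumed visit-1 shifts of 0.25, 0.5 or 1 within-person SD. Estimates stay essentially unbiased if orders are balanced. The power loss at 40 participants ranges from under one point to about 12 points, and the upper end depends on a large shift shared by all products. In logistic models the effect is attenuation of the product coefficient. Aim 1 nicotine-delivery conclusions are unlikely to change.

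For Aim 2, a residual variance from the unadjusted model would be too large by about 2%, 9% or 36%. It would oversize a later trial only if that trial adjusts for visit but reuses the unadjusted figure.

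The mechanism and its direction are certain. The size is not, because every visit shift used here is an assumption.

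**What to change.** In Statistical Considerations, write:

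> Models for outcomes with one value per visit (including AUC and Cmax, and logistic models of intentions) include product and visit number (1, 2, 3, categorical) as fixed effects, with a random subject effect.

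For craving, withdrawal or plasma values analysed at the six within-visit times, either reduce them to one value per visit, or also add time and a random visit-within-subject effect. The visit term alone does not give valid standard errors there.

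The cost is wording only, since visit number is known from the randomisation. The term uses 2 of 78 residual degrees of freedom (n = 40) or 2 of 28 (n = 15). If there is no visit effect, the two-sided 5% critical value rises by 0.04% or 0.35%. With an assumed 20% random dropout, the term adds on average 0.2% (n = 40) or 0.5% to 0.9% (n = 15) to the standard error.

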Interested participants will fill out a brief questionnaire to confirm eligibility either online or over the phone with research staff. Participants will be asked a series of questions regarding their tobacco product usage, health status, willingness to travel to Columbus for study visits, and brief demographic and contact information. Research staff will review the screener questionnaire for eligibility and inform participants if they are eligible for this study or not. Research staff will provide a study overview, discuss study procedures, and ascertain participant interest. Should the participant wish to proceed, research staff will schedule the first visit and communicate IRB-approved guidance, such as the CTR address and the need for subjects to abstain from tobacco products for 12 hours prior to the study visit. Participants will be advised that each research visit must be scheduled 2 or more days apart and that they must bring their own brand of cigarettes to the study visits in case they are randomized to smoke cigarettes at a particular visit.

Clinic Visits

Aim 1: Participants will be invited to the CTR to complete study procedures. At visit 1, informed consent will be collected. During visits 1-3, participants will complete an exhaled CO test, take a pregnancy test if applicable, a line will be placed for IV blood draw by the staff research nurse for IV blood draws throughout the course of the study visit, and be asked to either smoke their usual brand or insert a 3mg or 6mg NP and then sit in the room for 60 minutes. At each visit, participants will be randomly assigned to use 3mg Wintergreen pouches, 6mg Wintergreen pouches or their own brand of cigarettes. Participants will be asked a series of 3 questionnaires before, during, and after each product is used. Blood draws will be collected from the line at 0 5, 15, 30, 60, and 90-minutes. 3mLs, or a little less than 1 teaspoon, of blood will be drawn at each timepoint.

Measures of craving and withdrawal relief will be assessed at each blood draw (see attached surveys). If a collection interval is not met there will be no draw retroactively. Participants will be assessed for AE throughout procedures and prior to leaving the visit.

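### Craving and withdrawal are scored six times a visit, but the plan does not say how the scores enter its single model or how the minute-0 score is used

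*Combined protocol and SAP*

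**What the plan says.** Under Study Procedures, the peri-intervention questionnaire paragraph says: "The QSU and MNWS surveys will be administered while at each blood draw interval of 0, 5, 15, 30, 60, and 90 minutes". The Clinic Visits text adds: "Measures of craving and withdrawal relief will be assessed at each blood draw". With three visits, each person has up to 18 scores per scale, and product changes only between visits.

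The whole analysis text is in Statistical Considerations. It plans "mixed effects regression models (with a random subject effect) to assess the main effects of product on plasma nicotine delivery, subjective effects", in linear or logistic form, with behavioural intentions as a further outcome and the same strategy in both aims. On covariates it says: "Models will control for age, sex, and other tobacco use if these features are not balanced by randomization". On missing data: "Missing data will not be imputed as likelihood-based linear mixed models will yield valid inference under missing at random assumptions". On checking: "Model assumptions will be checked, and variables will be transformed as needed".

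A use for the minute-0 value is given only for nicotine: "This blood draw will also be used to establish baseline plasma nicotine levels to estimate total nicotine delivery". Nothing comparable is said for craving or withdrawal. No time term, product-by-time term, visit-within-subject effect, within-visit covariance or per-visit summary is named for these scales.

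**The concern.** Six scores from one visit are not six independent observations of a product. Whatever makes one visit different (sleep, stress, how well the person abstained) moves all six together, and a random subject effect does not absorb it. Craving may also change over the 90 minutes, and with no time term that movement goes into the residual. The two faults pull the standard error in opposite directions.

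Collapsing to one value per visit avoids this. The question then is which value, and whether the pre-use score is averaged in, subtracted or used as a covariate. The covariates that are named describe the person, not the visit. With complete data in the linear model they leave the product contrast unchanged.

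Two things are at stake. First, the plan doubles its sample from the 20 used in the power statement to 40, partly for the sake of subjective outcomes, and an inefficient summary can use up much of that increase. Second, Aim 2's 15 participants are there to supply effect-size data for later studies, and such data should not carry wrong standard errors or a diluted effect.

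**Working it through.** **The plan's own figures.** The 84% and 99% power (n = 20, alpha 0.017, which is 0.05/3 rounded) concern total nicotine delivery and maximum concentration. No SD is given, so they cannot be reproduced. Both outcomes have one value per visit, so they do not bear on this point. No power or precision is stated for craving or withdrawal.

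**Inputs.** From the documents: 3 visits, 6 times per visit, n = 40 and 15. Assumed, because the documents give nothing for these scales:
- rho is the share of within-person variance common to one visit, set at 0.1, 0.3 and 0.5. Within-person variance is scaled to 1, so visit variance is rho and residual variance is 1 - rho.
- Trend SD is the SD of the average time course over the six times, in within-person SDs.
- Alpha 0.017 two-sided is borrowed from the nicotine power statement.

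**If the 18 scores enter as rows.** With T = (trend SD)²,

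model variance / true variance = [(12 rho + 17(1 - rho) + 18T) / 17] / [6 rho + (1 - rho)].

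This equals 1 only when T = 5 rho, that is at trend SD = sqrt(5 rho): 0.71, 1.22 and 1.58 for the three values of rho.

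Example at rho 0.3, where the true term is 1.8 + 0.7 = 2.5:
- No trend: model (3.6 + 11.9)/17 = 0.912; SE ratio sqrt(0.912/2.5) = 0.604. The critical value 2.387 acts as 2.387 × 0.604 = 1.44, so false positives are 14.9%.
- Trend SD 1.5: model (15.5 + 40.5)/17 = 3.294; SE ratio sqrt(3.294/2.5) = 1.148. The critical value acts as 2.74, so false positives are 0.6%.

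Simulation (20,000 trials per setting, n = 40, no time term, nominal 1.7%):

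| Trend SD | rho 0.1 | rho 0.3 | rho 0.5 |
|---|---|---|---|
| 0 | 5.4% | 15.3% | 23.7% |
| 0.5 | 3.0% | 10.3% | 17.7% |
| 1.0 | 0.6% | 3.6% | 7.7% |
| 1.5 | 0.03% | 0.7% | 2.2% |

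Adding a time term alone returns about 5/15/24% at any trend, because the visit-level correlation is still unmodelled. Results at n = 15 are within one percentage point.

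**If each visit gives one value.** Assume an equal effect at all five post-use times. The variance per visit value, rescaled where the summary shrinks the effect, is:
- six-score mean: [rho + (1 - rho)/6] × 36/25, since including minute 0 shrinks the effect to 5/6;
- mean of minutes 5-90: rho + (1 - rho)/5;
- change from minute 0: 1.2(1 - rho);
- mean of minutes 5-90 adjusted for minute 0: rho + (1 - rho)/5 - rho².

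At rho 0.3 these are 0.60, 0.44, 0.84 and 0.35. Dividing each by the adjusted value gives the relative number of people needed. Power is by noncentral t, with noncentrality 0.4/sqrt(2V/40) for a 0.4 SD effect. At rho 0.3 the adjusted analysis has 0.4/sqrt(0.70/40) = 3.02, which gives 72%.

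| Value per visit | People needed, rho 0.1/0.3/0.5 | Power, n = 40 |
|---|---|---|
| Minutes 5-90, adjusted | 1 / 1 / 1 | 84 / 72 / 72% |
| Minutes 5-90, unadjusted | 1.04 / 1.26 / 1.71 | 82 / 60 / 45% |
| Six-score mean | 1.33 / 1.71 / 2.40 | 71 / 45 / 32% |
| Change from minute 0 | 4.00 / 2.40 / 1.71 | 24 / 32 / 45% |

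The six-score mean and the change score are equally efficient at rho 0.40, so neither is a safe default.

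**Does the adjusted analysis hold its level?** In simulation under a random subject effect, with t on 2n - 3 degrees of freedom (77 and 27), it rejected 1.4-2.0% at nominal 1.7%. With a Wald z test it rejected 2.3-2.7% at n = 15, so a small-sample method is needed.

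**The case against.** The strongest reply is that this treats silence as an error. Nothing says the scores will be rows. Speaking of relief hints at a change score, the minute-0 draw serves a per-visit nicotine summary, and the power statement uses per-visit values. The missing-data sentence fits rows, because a missed time point is then just a missing row ("If a collection interval is not met there will be no draw retroactively"), but it does not settle the matter. This objection stands. A reader might infer that the trial will have inflated false positives, and the documents do not support that. Even under rows the error could run the other way: people arrive after at least 12 hours' abstinence and then use nicotine, so a marked time trend is plausible.

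A reader might also infer that any valid summary wastes a large share of the sample. That is too strong. The ordinary mean of minutes 5-90 costs only 4% more people at rho 0.1, and nothing in the plan says a pre-use score would be averaged into the outcome.

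The equal-effect assumption can also be challenged. Hypothesis 1a expects slower nicotine delivery from pouches than from cigarettes, so craving differences may vary by minute and a flat mean could dilute them. That stands too, and it is why the fix offers a model with time.

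The assurance on model checking does not answer the point, since it names neither a visit effect nor a time term. Likelihood methods for missing data need a correct covariance model; they do not supply one.

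**Conclusion.** The point holds as a gap in specification with real consequences, and it should be fixed. Fitted to rows, the stated model gives wrong product standard errors except near trend SD = sqrt(5 rho), and the direction is unknown. Used on one value per visit, it is valid but gives up precision that a score already collected would provide: 1.04-1.71 times the people for the post-use mean, 1.33-2.40 for the six-score mean and 4.00-1.71 for change, as rho runs from 0.1 to 0.5.

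The omission itself is certain from the text. Every size above rests on assumed variances and, for power, on an effect equal at every post-use time. That minute 0 precedes product use is inferred from the order of procedures, not stated.

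The scope is limited. Subjective effects are listed as exploratory objectives, and craving and withdrawal appear in no numbered hypothesis. A reader might infer that the nicotine results or the stated power are in doubt. They are not, because total delivery and maximum concentration have one value per visit.

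**What to change.** For QSU and MNWS, state that the outcome is the post-use scores (minutes 5-90), adjusted for that visit's minute-0 score and the person's mean minute-0 score, in one of two forms:
- one mean per visit under the planned random subject effect, tested with Kenward-Roger or Satterthwaite degrees of freedom; or
- where time points are missed or product effects may differ by minute, rows with time, product-by-time and a random visit-within-subject effect.

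Name which form is the main one before data are examined, and state that minute 0 is scored before product use.

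The cost is a few sentences and no new data. When the time trend is small, intervals will be wider than the row-level ones. At rho 0.3 with no trend, simulated power is 71% against a nominal 80%, but that 80% comes with a false-positive rate of about 15%. A per-visit mean also hides the time course, which the second form shows.
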